1.3 Protocol Amendment #1 Summary of Changes

This document describes the changes in reference to the Protocol Incorporating Amendment No. 1.

The primary purpose of this amendment is to update the protocol regarding responsible medical officer contact, clarify Exclusion Criteria #4, Company Confidential , add assessment of GAS approach, and revise interim analysis criteria. Other minor changes in procedures are proposed. Minor grammatical and editorial changes are included for clarification purposes only. Full details regarding the text changes are given in Appendix E, including detailed rationale. The following is a summary of the changes made in the amendment:

- Updated responsible medical officer and protocol signatories.
 - Justification: Change in personnel.
- Clarified Exclusion Criteria #4.
 - Justification: The intent of this criteria is to exclude subjects who currently have significant risk of suicide (according to the investigator's clinical judgment), or made an actual suicide attempt in the previous 6 months prior to Screening, or within the same time frame have had active suicidal ideation with some intent to act (item 4 of CSSRS) or have had active suicidal ideation with specific plan and intent to act (item 5 of CSSRS). A lifetime "yes" answer to items 4 and 5 will not exclude the subject, but a "yes" answer to past 6 months for items 4 and 5 is exclusionary.
- Added assessment of Clinician and subject satisfaction with the GAS approach as a method for establishing treatment goals, evaluating progress towards treatment goals, and improving communication between clinicians and patients.
 - Justification: To assess the GAS approach in clinical practice and to guide future GAS work.
- Company Confidential
 - Company Confidential Information
- Clarified Interim Analysis criteria.
 - Justification: Analysis will be conducted once 60 subjects have completed, but enrollment will not be stopped.
- Correction of inconsistencies within the original protocol.

INVESTIGATOR AGREEMENT

I confirm that I have read and that I understand this protocol, the Investigator's Brochure, package insert, and any other product information provided by the sponsor. I agree to conduct this study in accordance with the requirements of this protocol and also to protect the rights, safety, privacy, and well-being of study subjects in accordance with the following:

- The ethical principles that have their origin in the Declaration of Helsinki.

Appendix E Detailed Description of Amendments to Text		

2.0 STUDY SUMMARY

Name of Sponsor:	Compound:		
Takeda Development Center Americas, Inc.	Vortioxetine		
Title of Protocol: An Open-Label, Single-Arm, Multicenter, Prospective, Phase 4, Interventional, Flexible Dose Study to Evaluate the Effectiveness of Vortioxetine on Goal Achievement After a Change in Antidepressant Medication for the Treatment of Subjects With Major Depressive Disorder	IND No.: 76,307	EudraCT No.: Not applicable	
Study Number: Vortioxetine-4003	Phase: 4		

Study Design:

This study is a nonrandomized, open-label, single-arm, multicenter, prospective, phase 4, interventional, flexible-dose study to determine the effectiveness of treatment with vortioxetine (per Trintellix United States [US] package insert) on subject goal achievement after a change in antidepressant medication for the treatment of major depressive disorder (MDD).

Potential subjects with MDD who are changing from another antidepressant to vortioxetine per routine care will be eligible to enroll. Subjects will determine treatment goals with their clinicians utilizing the Goal Attainment Scale (GAS) Methodology adapted for an MDD population. The subject and clinician will work to establish 3 goals at Baseline. One goal will be determined based on the subject's self-defined objectives. Two goals will be selected from the following predefined categories representing MDD residual symptoms, antidepressant side effects, and common reasons for changing antidepressant medication, including but not limited to:

MDD Domains	Psychological	Motivation	Emotional	Physical/ Functional	Cognition
Predefined Goal Categories:	Depressed mood Anxious mood	Lack of motivation	Low self esteem Anhedonia	Fatigue Insomnia Muscle tension Sexual dysfunction Weight gain	Problems concentrating Short-term memory problems Difficulty staying focused Difficulty paying attention Problems thinking clearly

This study is comprised of up to a 3-week Screening Period, followed by a 12-week Treatment Period and a 4-week Safety Follow-up Period. Study visits will occur at Baseline (Day 1), and Weeks 2, 4 (Telephone), 6, 9 (Telephone), and 12. This study will enroll approximately 120 subjects and will be conducted at approximately 25 sites in the United States. The investigator or the investigator's designee will access the Interactive Response Technology (IxRT) at Screening to obtain the subject study number. At the Baseline Visit, if the subject has satisfied all of the inclusion criteria and none of the exclusion criteria for enrollment, the subject will be enrolled using the IxRT. Subjects will be instructed on when to take the first dose of study drug. The dosing (both initial and adjustments) will be determined by the investigator or designee as per routine clinical practice and per approved Trintellix labeling.

Subjects who discontinue or who are withdrawn prior to study completion will come to the site for an Early Termination Visit as soon as possible and will be contacted for a Safety Follow-up 4 weeks after the last dose of study medication.

A futility analysis may be performed at an interim analysis after approximately 60 subjects have completed the study.

Primary Objective:

To determine the effectiveness of treatment with vortioxetine on subject goal achievement after a change in antidepressant medication for the treatment of MDD.

Secondary Objectives:

To determine the effectiveness of treatment with vortioxetine on depressive symptoms/outcomes, clinical global impression, cognitive impairment, and quality of life in subjects with MDD.

Exploratory/Additional Objectives:

- To determine the effectiveness of treatment with vortioxetine on cognitive performance and functionality in subjects with MDD.
- To determine the effectiveness of treatment with vortioxetine on work performance in subjects with MDD.
- To determine the effectiveness of treatment with vortioxetine on general health status and well being in subjects with MDD.
- To assess health care utilization and the safety and tolerability of vortioxetine in subjects with MDD.

Safety Assessments

Safety and tolerability of vortioxetine will also be evaluated using the following general assessments:

- Adverse events (AEs).
- AEs leading to discontinuation.
- Weight.
- Columbia-Suicide Severity Rating Scale (C-SSRS).

Subject Population: Men and women between the ages of 18 and 65 years, inclusive, with a primary diagnosis of MDD, who have previously been treated within 6 weeks of Screening or are currently being treated for a major depressive episode (MDE) with an approved antidepressant for 6 weeks or longer at an adequate dose. The change in antidepressant medication will be based on the investigator's judgment in collaboration with the subject's level of dissatisfaction with their current or recent antidepressant treatment (ie, residual mood symptoms, intolerable side effects). Subjects currently on an antidepressant at Screening will be discontinued in a manner that is consistent with labeling recommendations and conventional medical practice. Enrollment caps may be implemented throughout the course of the study based on the patient reported outcome (ie, Patient Health Questionnaire-9 [PHQ-9] and Perceived Deficits Questionnaire-Depression [PDQ-D]) scores at Baseline.

Number of Subjects:	Number of Sites:
Approximately 120 subjects	Estimated total: approximately 25 sites in the United States
Dose Levels:	Route of Administration:
Vortioxetine 5, 10, or 20 mg once daily as per Trintellix US Package Insert	Oral
Duration of Treatment:	Period of Evaluation:
12-week Treatment Period	Up to 19 weeks including a 3-week Screening Period (maximum of 21 days), a 12-week Treatment Period and 4-week Safety Follow-up Period

Main Criteria for Inclusion:

- 1. Subject is a man or woman between 18 to 65 years, inclusive, and able to read and understand English.
- 2. Subject suffers from MDD as the primary psychiatric diagnosis.
- 3. Subject has been or is currently being treated with an approved antidepressant (monotherapy) for 6 weeks or longer at an adequate therapeutic dose as per investigator judgment.
- 4. The antidepressant treatment must be ongoing or have been discontinued within 6 weeks of Screening. Subjects currently on an antidepressant at Screening will be discontinued in a manner that is consistent with labeling recommendations and conventional medical practice.
- 5. Subject is considered appropriate for a change in antidepressant medication based on investigator judgment in collaboration with the subject.
- 6. Subject has scores on PHQ-9 ≥5 and Clinical Global Impression Scale-Severity (CGI-S) ≥4 at Screening.
- 7. In the opinion of the investigator, the subject is capable of understanding and complying with protocol requirements.
- 8. The subject signs and dates a written, informed consent form and any required privacy authorization prior to the initiation of any study procedures.
- 9. A female subject of childbearing potential who is sexually active agrees to routinely use adequate contraception from signing of the informed consent throughout the duration of the study and for 30 days after the last dose of study drug.

Main Criteria for Exclusion:

Any subject who meets any of the following criteria will not qualify for entry into the study:

- 1. Subject has any current psychiatric disorder other than MDD (except nonprimary concurrent anxiety), other illness or condition which may compromise the study in the opinion of the investigator.
- 2. The subject has discontinued prior antidepressant treatment greater than 6 weeks prior to Screening.
- 3. Subject is considered to be at imminent risk for hospitalization due to severe depression in the opinion of the investigator. Recent hospitalization due to MDD within 3 months prior to Screening is also exclusionary.
- 4. The subject has a significant risk of suicide according to the investigator's clinical judgment or has made an actual suicide attempt in the previous 6 months prior to Screening or scores "yes" on Items 4 or 5 in the past 6 months on the Suicidal Ideation section of the C-SSRS.
- 5. The subject is considered to be treatment resistant, defined as patients with MDD who have not responded to 2 or more different antidepressants monotherapy studies of adequate dose and duration (6 weeks or longer) in their current episode. History of only responding to either combination or augmentation therapy in previous MDEs is also considered evidence of treatment resistant depression.
- 6. The subject has received any investigational compound within 30 days prior to Screening or 5 half-lives prior to Screening, whichever is longer.
- 7. The subject has previously or is currently participating in this study or another vortioxetine or LuAA21004 study.
- 8. The subject has participated in 2 or more interventional clinical studies in the year prior to Screening, or has participated in a clinical study for a psychiatric condition that is exclusionary per this protocol.
- 9. The subject is an immediate family member, study site employee, or is in a dependent relationship with a study site employee who is involved in conduct of this study (eg, spouse, parent, child, sibling).
- 10. The subject has 1 or more of the following:
 - a) Current or history of: manic or hypomanic episode, schizophrenia or any other psychotic disorder, including schizoaffective disorder, major depression with psychotic features, bipolar depression with psychotic features, obsessive compulsive disorder, mental retardation, organic mental disorders, or mental disorders due to a general medical condition as defined in The Diagnostic and Statistical Manual of Mental Disorders,

Fifth Edition as determined by the investigator.

- b) Current diagnosis or history of alcohol or other substance abuse or dependence (excluding nicotine or caffeine). The subject must have a negative urine drug screen at Screening and Baseline, this includes benzodiazepines and opiates (including oxycodone) for which there is no prescription.
- c) Presence or history of a clinically significant neurological disorder (including epilepsy) as determined by the investigator.
- d) Neurodegenerative disorder (Alzheimer disease, Parkinson disease, multiple sclerosis, Huntington disease, etc).
- 11. The subject has received vortioxetine previously, or the subject has a history of hypersensitivity or allergies to vortioxetine or any of its components.
- 12. Subjects receiving or who have started receiving formal cognitive or behavioral therapy, systematic psychotherapy within 30 days from screening or plan to initiate such therapy during the study (marital therapy, and bereavement counseling are allowed).
- 13. The subject is receiving excluded medications or it is anticipated that the subject will require treatment with at least 1 of the disallowed concomitant medications during the study.
- 14. The subject has a clinically significant unstable illness as determined by the investigator.
- 15. The subject has a known history of acute narrow-angle glaucoma or is at risk of acute narrow-angle glaucoma.
- 16. The subject has a known unstable thyroid disorder or a thyroid-stimulating hormone value outside the normal range based on medical history that is deemed clinically significant by the investigator.
- 17. The subject has clinically significant abnormal vital signs as determined by the investigator.
- 18. The subject has active hepatitis B or a known history of hepatitis C virus.
- 19. The subject has a known history of human immunodeficiency virus infection.
- 20. The subject has a history of gastric bypass.
- 21. The subject has a disease or takes medication that, in the opinion of the investigator, could interfere with the assessments of safety, tolerability, or effectiveness.
- 22. If female, the subject is pregnant or lactating or intending to become pregnant before, during, or within 1 month after participating in this study; or intending to donate ova during such time period.

Main Criteria for Evaluation and Analyses:

• **Primary endpoint**: Proportion of subjects who achieve their identified goals as demonstrated by an outcome GAS Score of >50 at Week 12.

• Secondary endpoints:

- Mean change from Baseline in total GAS Score at Week 6 and Week 12.
- Change from Baseline in depression severity as measured by the PHQ-9 Score at Week 6 and 12.
- Change from Baseline in perceived cognitive deficits and cognitive function as measured by the PDQ-D at Weeks 6 and 12.
- Change from Baseline in Quality of Life Enjoyment and Satisfaction Scale (Q-LES-Q) Score at Week 12.
- Change from Baseline in 5-item World Health Organization Well-Being Index (WHO-5) Score at Week 12.
- Change from Baseline in CGI-S at Week 12.
- Clinical Global Impression Scale-Improvement (CGI-I) Score at Week 12.

• Exploratory/Additional: Company Confidential Information

Safety Assessments

Safety and tolerability of vortioxetine will also be evaluated using the following general assessments:

- AEs
- AEs leading to discontinuation.
- Weight.
- C-SSRS.

Statistical Considerations:

Primary Effectiveness Analysis:

• The primary effectiveness variable will be the proportion of subjects who changed to treatment with vortioxetine who achieve their identified goals at Week 12 (ie, GAS Score ≥50). The GAS yields a norm-based score (standardized to a mean of 50, SD of 10) at Baseline and for each follow-up; the change from score at Baseline will be summarized. The responder rate at Week 12 and the change in total GAS Score at each follow-up will be assessed by the 95% CI. Similar analyses will be done for other endpoints.

Secondary Effectiveness Analysis:

A paired t-test will be applied to the change from Baseline for the GAS Score. For the secondary endpoints of outcomes measures on PHQ-9, PDQ-D, Q-LES-Q Score, WHO-5 Score, and CGI-S total scores and changes from Baseline will be summarized by each time point of Baseline and Week 12 with paired t-tests. Tests of significance will be 2-tailed with alpha level at 0.05. CGI-I Scores will be summarized at Week 12 using descriptive statistics.

Additional analyses:

Company Confidential Information

Safety Analysis:

The safety data will be summarized. AEs will be reported throughout the study. The definition of treatment-emergent AEs will be provided in the statistical analysis plan. AEs will be coded using the Medical Dictionary for Regulatory Activities and will be summarized by system organ class and preferred term. AEs that were reported more than once by a subject during the same period will be counted only once for that subject and at period of the maximum severity.

Sample Size Justification:

As no formal hypothesis testing is performed for the primary endpoint, the purpose of sample size estimation is to determine the adequate sample size needed to provide a precise estimate for the response rate (GAS Score \geq 50) with 95% CIs. Conservatively estimating that 50% of subjects will be responders (GAS \geq 50) and that 100 subjects will complete the study, CIs will be \pm 0.098 around the point estimate (proportion of responders).

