The investigator or the investigator's designee will access the Interactive Response Technology (IxRT) at Screening to obtain the subject study number. At the Baseline Visit, if the subject has satisfied all of the inclusion criteria and none of the exclusion criteria for enrollment, the subject will be enrolled using the IxRT. Subjects will be instructed on when to take the first dose of study drug. The dosing (both initial and adjustments) will be determined by investigator or designee as per routine clinical practice and per approved Trintellix labeling. Subjects will determine treatment goals with their clinicians using the GAS adapted for an MDD population. The subject and clinician will work to establish 3 goals at Baseline. One goal will be determined based on the subject's self-defined objectives. Two goals will be selected from the following predefined categories representing MDD residual symptoms, antidepressant side effects, and common reasons for a change in antidepressant medication, including but not limited to:

[figure not shown]
MDD Domains	Psychological	Motivation	Emotional	Physical/ Functional	Cognition
Predefined goal categories:	-Depressed mood -Anxious mood	-Lack of motivation	-Low self esteem -Anhedonia	-Fatigue -Insomnia -Muscle tension -Sexual dysfunction -Weight gain	-Problems concentrating -Short term memory problems -Difficulty staying focused -Difficulty paying attention -Problems thinking clearly

[figure not shown]
A prepopulated list of categories will be provided in the structured guidance for goal assessment, including behavioral examples describing goals and observable benchmarks to help clinicians set the appropriate goals with subjects. Goals will be set at Baseline/Visit 1. Progress will be evaluated at the Week 6 visit. At the Final Visit the goals will be assessed based on levels of achievement on a 5-point scale. Investigators will be trained on goal setting/goal assessment and monitored for ability in key domains of goal setting (eg, attainability of goals, use of observable objectives and benchmarks, equidistance of scaling, general level of difficulty, goal differentiation, and overall quality).

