7.0 SELECTION AND DISCONTINUATION/WITHDRAWAL OF SUBJECTS

All entry criteria, including test results, need to be confirmed prior to enrollment or first dose.

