7.1 Inclusion Criteria

Subject eligibility is determined according to the following criteria prior to entry into the study:

- 1. Subject is a man or woman, aged 18 to 65 years, inclusive, and able to read and understand English.
- 2. Subject suffers from MDD as the primary psychiatric diagnosis.
- 3. Subject has been or is currently being treated with an approved antidepressant (monotherapy) for 6 weeks or longer at an adequate therapeutic dose. Subjects currently on an antidepressant at Screening will be discontinued in a manner that is consistent with labeling recommendations and conventional medical practice.
- 4. The subject's antidepressant treatment must be on-going at time of Screening, or have been discontinued within the 6 weeks prior to Screening.
- 5. Subject is considered appropriate for a change in antidepressant medication based on investigator judgment in collaboration with the subject.
- 6. Subject has scores on PHQ-9 \geq 5 and CGI-S \geq 4.
- 7. A female subject of childbearing potential who is sexually active agrees to routinely use adequate contraception* from signing of the informed consent throughout the duration of the study and for 30 days after the last dose of study drug.
- 8. In the opinion of the investigator, the subject is capable of understanding and complying with protocol requirements.
- 9. The subject signs and dates a written, informed consent form and any required privacy authorization prior to the initiation of any study procedures.

*Definitions and acceptable methods of contraception and Contraception and Pregnancy Avoidance Procedure are defined in Section 9.1.9. Pregnancy reporting responsibilities are defined in Section 9.1.10.

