Appendix A Schedule of Study Procedures

	Screening	Treatment						
	Visit 1 (a)	Baseline Visit 2 (a) Day 1	Visit 3 Wk 2	Telephone Contact Visit 4 Wk 4	Visit 5 Wk 6	Telephone Contact Visit 6 Wk 9	End of Study Visit 7 Wk 12 /Early Termination	Visit 8 Wk 16
	Days -21 up to -1	Day 1	Day 15 (±3 Days)	Day 29 (±3 Days)	Day 43 (±5 Days)	Day 64 (±5 Days)	Day 85 (±5 Days)	Day 113 (± 7 Days)
Informed consent	X							
Eligibility criteria	X	X						
Demographics, medical history, medication history	X							
UDS (b)	X	X						
MDD diagnosis confirmed by investigator judgment, antidepressant medication history & disease history	X							
Height and weight (c)	X	X					X	
Hematology and limited serum chemistry		X					X	
PGx sample collection (d)		X					X	
Concurrent medical conditions	X	X						
Concomitant medications		X	X	X	X	X	X	X
Vital signs	X							
GAS assessment		X			X		X	
PHQ-9	X	X			X		X	
Q-LES-Q		X					X	
PDQ-D		X			X		X	
Company Confidential Inform	ation							
Company Confidential Inforn								
Company Confidential Inforn	nation							
C-SSRS	X	X	X		X		X	
Company Confidential Inforn	nation							
WHO-5		X			X		X	
CGI-S	X	X	X		X		X	
CGI-I			X		X		X	

Footnotes are on last table page.

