7.8.4 Analyses for Secondary and Additional Endpoints

For the secondary endpoints of outcome measures of GAS Score, PHQ-9, PDQ-D, Q-LES-Q Score, WHO-5, and CGI-S, total scores and changes from Baseline will be summarized by each time point of Baseline, Week 6 (as appropriate) and by each time point of Baseline and Week 12. These changes from Baseline will be analyzed using paired t-tests. Also, for each of the outcome measurements, change from Baseline at Week 12 will be analyzed using paired t-tests. Tests of significance will be 2-tailed with alpha level at 0.05. CGI-I Scores will be summarized at Week 12 using descriptive statistics.

Company Confidential Information

Additionally, data will be summarized by the following response and remission rates, respectively:

- response defined on the PHQ-9 ($\geq 50\%$ reduction in total score from Baseline) at week 6 and week 12
- response based on CGI-I (CGI-I score of ≤ 2) at week 6 and week 12
- remission defined on PHQ-9 (PHQ-9 score of ≤ 4) at week 6 and week 12
- remission based on CCI-S (CGI-S score of ≤ 2) at week 6 and week 12.

Company Confidential Information

In order to assess Goal Attainment Scaling as a sensitive, reliable measure of response to drug treatment for depression, a series of analyses will be performed to examine the GAS approach against other measures assessed in the study, as well as to evaluate change in GAS scores over time. A full description of the analysis will be described in a separate validation plan.

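### Inclusion criterion 6 does not consistently name the visit at which PHQ-9 ≥5 and CGI-S ≥4 must hold, and the SAP's PHQ-9 remission rate has no Baseline condition to absorb the ambiguity

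*Protocol*

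**What the plan says.** **Entry rule.** Synopsis (Protocol 2.0), item 6: "Subject has scores on PHQ-9 ≥5 and Clinical Global Impression Scale-Severity (CGI-S) ≥4 at Screening". Protocol 7.1, item 6, opens "Subject has scores on PHQ-9" and gives the same two cut-offs, but names no visit.

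**When eligibility is judged.** Protocol 7.0: "All entry criteria, including test results, need to be confirmed prior to enrollment or first dose". The lead-in to 7.1: "Subject eligibility is determined according to the following criteria prior to entry into the study". Section 6.1 places enrolment at Baseline: "At the Baseline Visit, if the subject has satisfied all of the inclusion criteria and none of the exclusion criteria for enrollment". Section 9.1.13 admits to treatment only subjects who meet every inclusion criterion. Appendix A schedules the eligibility check, the PHQ-9 and the CGI-S at both Screening and Baseline. Section 9.3.1 allows up to 21 days between the visits. It also allows them to be combined, in which case a procedure due at both is done once.

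**Analysis.** SAP 7.8.4 lists "remission defined on PHQ-9" as a score of 4 or less at Weeks 6 and 12, and PHQ-9 response as a reduction of at least 50% from Baseline. CGI-S remission is a score of 2 or less. None of these carries a Baseline condition. SAP 7.1 defines Baseline as the last value before first dose and bases proportions on subjects with non-missing responses. SAP 7.8 uses the FAS for all efficacy analyses, and the FAS definition in SAP 7.2 has no severity requirement.

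**The concern.** The entry floor (5) lies one point above the remission cut-off (4), and the score that qualifies a subject need not be the score from which the SAP measures. If the floor applies at Screening only, a subject can qualify with PHQ-9 of 5 or 6, score 4 at Baseline, stay at 4, and be tabulated as in remission at Weeks 6 and 12.

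Protocol 6.2.1 justifies the single arm by letting each subject act as their own control against Baseline. A remission with no change from Baseline does not fit that rationale, and there is no comparator arm in which the same artefact would appear and cancel.

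There is also an operational side. About 25 sites could apply item 6 differently, and Protocol 14.2 allows no exemptions from entry criteria. The same subject is eligible on one reading and a protocol deviation on the other.

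**Working it through.** **1. The plan's own figure.** The only design figure is the ±0.098 half-width in SAP 6.0. With p = 0.50 and n = 100: 1.96 × √(0.50 × 0.50 / 100) = 0.098. It reproduces. It concerns the GAS responder proportion and does not involve criterion 6.

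**2. The passages side by side.**

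| Place | Visit for the PHQ-9/CGI-S floor |
|---|---|
| Synopsis, item 6 | Screening |
| 7.1, item 6 | none named |
| 7.0; 7.1 lead-in; 9.1.13 | criteria met and confirmed before enrolment, entry or treatment; no visit named for the scores |
| Appendix A | eligibility, PHQ-9 and CGI-S at both visits; no statement that the Baseline scores must meet the floor |

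The protocol names both visits where it wants both: exclusion criterion 10b requires a negative urine drug screen at Screening and Baseline. That favours a Screening-only reading of the synopsis. The undated item 6, taken with the Baseline eligibility check, favours re-applying the floor. Neither is conclusive. At a combined visit one score serves both purposes and the gap cannot arise.

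**3. Effect on the PHQ-9 remission rate if the floor is Screening-only.** Let f be the share of analysed subjects with Baseline PHQ-9 ≤4, p the remission rate in the others, and s the share of the f subjects who are at ≤4 at the analysis visit.

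Reported rate = (1 − f)p + f·s, so the shift is f(s − p).

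The documents give none of these inputs. Assumed ranges: p from 0.20 to 0.40, s from 0.5 to 1.0.

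| f | smallest shift (p = 0.40, s = 0.5) | largest shift (p = 0.20, s = 1.0) |
|---|---|---|
| 1% | +0.1 points | +0.8 points |
| 2% | +0.2 | +1.6 |
| 5% | 0.05 × 0.1 = +0.5 | 0.05 × 0.8 = +4.0 |
| 10% | +1.0 | +8.0 |

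The shift is upward only when s exceeds p, which holds throughout these ranges. With Baseline PHQ-9 ≥5 required in the denominator, f = 0 and the shift is 0.

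**4. How readily a low Screening score could fall to ≤4.** Assume the difference between two visits has an SD of 3 points (range 2 to 4) with no true change.

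- If the expected second score equals the first, P(≤4) = Φ((4.5 − b)/SD). For b = 5 this is Φ(−0.5/3) = 0.43 (0.40 to 0.45).
- That ignores regression to the mean. Assume a population SD of 5. A difference SD of 3 then implies a correlation of 1 − 9/(2 × 25) = 0.82 and a conditional SD of 5 × √(1 − 0.82²) = 2.86. With a population mean of 10, the expected second score is 10 + 0.82 × (5 − 10) = 5.9, and Φ((4.5 − 5.9)/2.86) = 0.31. With a mean of 14 it is 14 + 0.82 × (5 − 14) = 6.62, and Φ((4.5 − 6.62)/2.86) = 0.23.

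These are chances for one subject who scored 5 at Screening. They are not shifts in a reported rate, and they take no account of the CGI-S requirement. They show only that the scenario is not far-fetched.

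**5. The 50% response rule at low Baseline scores.** Whole points needed: Baseline 1 or 2 needs 1; 3 or 4 needs 2; 5 needs 3. At Baseline 0 a percentage reduction is undefined.

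**The case against.** The strongest reply is that the protocol already closes the gap. All entry criteria must be confirmed before enrolment or first dose, only subjects meeting every criterion may enter treatment, and eligibility is checked again at Baseline with both scales repeated. This has real weight. A reader might infer from the synopsis that subjects already at the remission cut-off are knowingly admitted, but the documents do not establish that. What survives is the ambiguity: a criterion dated to Screening is still satisfied by the Screening score when confirmed later, and no passage says the Baseline scores must meet the floor.

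The second reply is that little rests on these rates. That is correct. Protocol 6.2.3 and SAP 5.0 describe the secondary endpoint assessments as confirmation with validated instruments. The PHQ-9 and CGI-S secondary endpoints are changes from Baseline, whereas the response and remission rates are additional summaries with no test specified. It would be wrong to read this point as bias in the confirmatory secondary endpoints.

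Two further inferences are not supported:

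- **Upward bias in PHQ-9 response.** A Baseline of 1 or 2 makes response easy in points, but a Baseline of 0 cannot improve, and a Baseline of 3 or 4 needs a two-point drop with little room below. The net direction is not shown.
- **Comparable exposure of CGI-S remission.** A subject would have to fall from ≥4 at Screening to ≤2 before first dose.

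It is also fair to say that a floor of 5 with remission at ≤4 is coherent in itself, that subjects switching for side effects may properly have low scores, and that enrolment caps on Baseline PHQ-9 are available. The caps are optional, however, and do not settle which visit item 6 means.

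**Conclusion.** The point holds as an unresolved ambiguity in the entry rule, combined with a remission definition that offers no protection if the Screening-only reading is applied. It is confined to subjects with separate Screening and Baseline visits. Its demonstrated effect is a possible inflation of the additional PHQ-9 remission summary: illustratively +0.5 to +4 points if 5% of analysed subjects start at ≤4, and proportionately less or more at other shares. That range rests on assumed values of p and s. The share itself is unknown and could be zero.

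The primary GAS endpoint, the ±0.098 precision and the definitions of the change-from-Baseline endpoints are not affected. The change is worth making because it is cheap and uses data already scheduled, not because the study's main conclusion is at risk.

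**What to change.** **Protocol.** Reconcile synopsis item 6, Sections 7.0, 7.1 and 9.1.13, and Appendix A so that item 6 names the visit or visits at which the scores must be met, and how this works at a combined visit. Which visit or visits apply is for the sponsor to decide.

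**SAP 7.8.4.** Report PHQ-9 remission among FAS subjects with Baseline PHQ-9 ≥5. Use the same denominator for PHQ-9 response, because a 50% reduction is undefined at Baseline 0. State the number excluded. This removes the artefact whichever entry reading the sites applied, including for subjects already enrolled. Because SAP 7.8 assigns all efficacy analyses to the FAS, word it as a defined FAS subset for these rates. A matching condition for CGI-S remission (Baseline CGI-S ≥3) is optional and would have little effect.

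**Cost.** A wording change in the protocol and a sentence or two in the SAP, with no new data. The downside is a slightly smaller denominator and possibly a slightly lower remission rate.
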